8.1 Missing Data

Missing data occurs when any requested data are not provided, leading to blank fields on the collection instrument. These data will be indicated by the use of a “blank” in subject listing displays. Answers such as “Not applicable” and “Not evaluable” are not considered to be missing data and should be displayed as such.

The primary safety endpoint is the TEAEs for C1-INH HAE subjects, and a result of zero TEAEs is considered a valid outcome, not missing data. The monitoring of reported AEs is performed throughout the study. If inconsistencies are detected, queries will be generated. Even if date or time of an AE will be completely or partially missing, it will be considered

treatment-emergent following the worst-case principle, unless the partial date clearly indicates that the AE started before the first administration of study treatment.

The details of handling missing data are presented in the corresponding sections of this SAP for respective analyses (eg, primary, and secondary safety analyses).

8.2 General Derived Variables

8.2.1 Reference Dates and Study Days

Reference dates are used to assign study periods relative to treatment ([Section 8.4](#)). The main reference date for safety and efficacy is the treatment start date, which will be used to calculate study day for those measures.

The respective study day will be calculated as (date of interest - reference date) + 1 if the date of interest occurs on or after the reference date. If the date of interest occurs before the reference date, then the study day will be calculated as (date of interest – reference date). There will be no study day zero.

For PK, the reference date is the treatment start date.

For the additional PK assessments performed for adolescents and the subset of CSL312-naïve subjects, the reference date/time is the start of administration of the Day 1 Visit dose for the subset of CSL312 naïve subjects and the Month 3 dose for adolescents. The respective study day relative to the reference date will be calculated for figures as (date of interest - reference date) if the date of interest occurs on or after the reference date.

The reference date/time for treatment while on AI will be derived based on the dosing data and the Autoinjector confirmation page of the eCRF, as the first recorded dose date/time with date on or after the date on the Autoinjector confirmation page.

8.2.2 Durations and Time to Event Data

Durations (eg, the duration of an AE) are calculated in days as:

- event end date – event start date + 1, if end time or start time not available.
- event end date / time – event start date / time, if both end time and start time available.

Thus, there will be no duration of 0. If an AE has missing or partially missing start or end date, no duration will be calculated.

For elapsed time (eg, the time to event), use:

- (event date – reference date) or
- event date / time – reference date / time, if time available.

Thus, an event which happens on the same date as the reference date will have an elapsed time of 0 if event time or reference time are not available.

To transform durations or elapsed times, which are calculated in days into weeks, divide the number of days by 7; to report in months, divide the number of days by 30.4375; to report in years, divide the number of days by 365.25. These algorithms return decimal numbers and ignore the actual numbers of days in the months or years (the calendar days) between start date and stop date. The "year" used in these algorithms is 365.25 days long, and the "month" is one twelfth of that year.

8.2.3 Baseline Definition

Baseline is defined as the most recent, non-missing value prior to first study drug administration in this study. Determination of the baseline value considers unscheduled visits during the Run-in and Screening Periods.

If the measurement of a variable is not made on a given subject prior to first study drug administration, the baseline value for that subject will be set to missing for that variable.

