4.1.1.2 Treatment Period

CSL312-naïve subjects will be eligible to exit the Run-in Period and enter the Treatment Period if they meet all the following criteria:

1. Participated in the Run-in Period for at least 1 month.

2. Experienced at least an average of 1 HAE attack per month during the Run-in Period (ie, experienced a total of at least 2 HAE attacks).
3. Do not have laboratory clinical abnormalities assessed as clinically significant by the investigator in results of hematology, chemistry, or urinalysis assessments performed during Screening.
4. C1-INH functional activity and antigen, and C4 antigen concentration levels have been verified at screening.

Note: Subjects with ≥ 2 times the upper limit of normal for aspartate aminotransferase (AST) and / or alanine aminotransferase (ALT) may be eligible for participation if there is an explanation for this laboratory result and if the results are not clinically significant.

Subjects who successfully complete Studies CSL312_2001 or CSL312_3001 according to their respective protocols may roll over directly from treatment in those trials and start this study at Treatment Day 1.

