8.6.3 Treatment Period (All CSL312_3001 Subjects and CSL312-naïve Subjects) for Original Protocol

8.6.3.1 Treatment Period Visit Day 1

CSL312-naïve subjects must complete all screening assessments, fulfill the eligibility criteria (ie, eligible subjects), and meet the Treatment Period entry criteria ([Section 4.1.1.2](#)).

For subjects who completed Study CSL312_3001 and choose to participate in Study CSL312_3002 (CSL312_3001 rollover subjects), assessments from Day 182 of Study CSL312_3001 will be used to fulfill assessments for Day 1 of Study CSL312_3002

(ie, the last study visit of CSL312_3001 and the first study visit of Treatment Period in CSL312_3002 occur on the same day).

If a subject did not participate in a Screening Visit (CSL312_3001 subjects), then a written informed consent / assent must be obtained before any study-specific assessments or procedures are performed at the first visit in the Treatment Period.

The following procedures / assessments will be conducted and documented:

- Written informed consent for subjects rolling over from Study CSL312_3001.
- Confirm eligibility for Treatment Period
- Perform physical examination.
- Record vital signs, including body weight and height.
- TSQM II (subjects ≥ 18 years).
- AE-QoL (subjects ≥ 18 years).
- WPAI:GH (subjects ≥ 16 years).

Note: Subjects rolling over from Study CSL312_3001 who have completed the AE-QoL and WPAI:GH as part of the last visit of Study CSL312_3001 will only need to complete the TSQM II at Day 1.

- Urine collection for urinalysis.
- Collection of blood to assess:
 - Hematology.
 - Biochemistry.
 - Coagulation.
 - Retention sample for HAE biomarkers (adults only).
 - PK / PD.
 - Immunogenicity.
- Collect urine for pregnancy test (for women of childbearing potential).
- PRO / eCOA tablet training

- Review eDiary instructions with subject
- Review eDiary data and assess / document HAE attacks.
- Confirm access to on-demand HAE medication.
- IRT CSL312 kit assignment.
- Accountability of CSL312

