8.6.4 Treatment Period (CSL312_2001 Subjects Only) for Original Protocol

8.6.4.1 Treatment Period: Day 1

For subjects who completed Study CSL312_2001 and choose to participate in Study CSL312_3002 (CSL312_2001 rollover subjects), assessments from Week 57 (Day 399) of Study CSL312_2001 will be used to fulfill assessments for Day 1 of Study

CSL312_3002 (ie, the last study visit of CSL312_2001 and the first study visit of Treatment Period in CSL312_3002 occur on the same day).

Written informed consent / assent must be obtained before any study-specific assessments or procedures are performed at the first visit in Treatment Period.

The following procedures / assessments will be conducted:

- Written informed consent.
- Confirm eligibility for Treatment Period.
- Perform physical examination.
- Record vital signs, including body weight and height.
- TSQM II (subjects ≥ 18 years).
- AE-QoL (subjects ≥ 18 years).
- WPAI:GH (subjects ≥ 16 years).

Note: Subjects rolling over from Study CSL312_2001 who have completed the AE-QoL and WPAI:GH as part of the last visit of Study CSL312_2001 will only need to complete the TSQM II at Day 1.

- Urine collection for urinalysis.
- Collection of blood to assess:
 - Hematology.
 - Biochemistry.
 - Coagulation.
 - Retention sample for HAE biomarkers (adults only).
 - PK / PD.
 - Immunogenicity
- Collect urine for pregnancy test (for women of childbearing potential).
- PRO / eCOA tablet training.
- Review eDiary instructions with subject.

- Confirm access to on-demand HAE medication.
- IRT CSL312 kit assignment.
- CSL312 accountability
- Subcutaneous administration of CSL312 dose by investigator or delegate or by the subject under the supervision of the investigator or delegate (after completion of physical examination and vital signs). Subjects will complete the Medication Dosing Diary on the eDiary after dosing at the site is complete.
- Record concomitant medications and therapies (type, dose, route, date, and time).
- Record AEs.

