On-demand HAE medication will be summarized as separate block within the summaries of prior and concomitant medication (as a “virtual” ATC class “On-demand HAE Medication”). The on-demand HAE medication will also be reported in their original ATC class.

Technical Note: On-demand HAE medications prior to Run-in Period are collected in the eCRF form ‘Concomitant and Prior Medications’ with Primary Indication as ‘Study Indication Acute HAE Treatment’. On-demand HAE medications on/after start of the Run-in Period are collected in a separate eCRF form ‘On-demand Treatment’. On-demand medication during the treatment period given for pre-procedure prophylaxis instead of an HAE attack is also documented on the CM and Prior Medication form with the indication “Study Indication (Pre-Procedure/Short Term HAE Prophylaxis”.

For rollover subjects, on-demand HAE medications for attacks that occurred during the Run-in Period of the lead-in study will be imported from the final analysis datasets of the respective lead-in study. Study day will be recalculated to be relative to the reference date for CSL312_3002.

Tables and listings will be provided for ATS.

A listing of prior/concomitant medication will be provided, including the flag for prior medication taken during the run-in period. Non-pharmacological procedures will be listed.

10 Efficacy Analyses

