10.3.2.1 Analysis of Quality of Life Endpoints

IGART

The number and percentage of subjects with each response for the IGART (none, poor, fair, good or excellent) as well as for the cumulative categories poor or better, fair or better, good or better will be presented by visit.

For the percentage of cumulative responses, a two-sided 95% CI will be presented. The Friedman test will be used to compare the percentage of subjects with good or excellent responses between study Visit Month 12, study Visit Month 24 and study Visit Month 36. The test will be exploratory with an alpha of 5%. The shift tables for SGART (described in [Section 10.2.1.5](#)) will be repeated for IGART.

WPAI:GH, TQSM and AE-QoL

Unlike for the other analyses in this SAP, the analyses described in this section will be only performed separately for treatment-naïve subjects and non-treatment-naïve subjects (see [Section 8.3.2](#)), without pooling them together.

For the WPAI:GH, TSQM, and AE-QoL, total and domain scores will be presented descriptively by study visit as well as the individual changes in scores between the baseline visit and subsequent visits.

Two-sided 95% CIs for the differences will be presented.

The proportion of subjects achieving a minimal clinically important difference (MCID) will be calculated for Baseline and Visit Month 24 and Visit Month 30 for the total and domain scores.

The MCID for the AE-QoL is defined as -6. For the WPAI:GH and the TSQM, the MCID will be estimated using the half SD approach which has been shown to approximate the threshold of discrimination for a clinically meaningful change. The SD at Baseline will be used to derive the MCID.

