11.5 Clinical Laboratory Evaluations

The laboratory tests in Section 8.1.1 of the protocol will be summarized as described in this section. Unscheduled visits will be handled as described in [Section 8.2.5](#). Definition of the baseline assessment is in [Section 8.2.3](#).

The test names and units from the central laboratory transfer will be used. The sequence and groupings in which parameters are provided will match Table 2 of the protocol.

Separate summary tables for hematology, biochemistry, coagulation, urinalysis, and immunogenicity tests will be produced.

Summaries to be produced are:

- Laboratory values and changes from baseline by scheduled study visit for continuous tests and number and percentages per category for categorical tests.
- The number and percentage of subjects with clinically significant laboratory findings reported as AEs by test and visit. Those will be identified through the eCRF form ‘Clinical Significant Safety Lab Data.’.

The percentages for categorical tests will be based on the number of subjects with non-missing values at each visit.

The presence of anti-CSL312 antibodies will be summarized descriptively by visit. This summary will include the number and percentage of subjects who experience anti-drug antibodies.

A laboratory value that is outside the reference range is either high abnormal (value above the upper limit of the normal [ULN] reference range) or low abnormal (value below the lower limit of the normal [LLN] reference range). An abnormal laboratory value is not necessarily of potential clinical interest.

Listings of laboratory data will include test name and unit along with normal range, the sampling date and time, the test result, an assessment whether the result is high (above normal range) or low (below normal range). Any comments to the laboratory test will be provided in a separate listing, if applicable.

A by-subject listing for laboratory abnormalities will be provided in the same format as the laboratory listings described above but only containing information about abnormal laboratory results and including the laboratory category.

Listings to be produced are:

- All laboratory values including flags for values outside the normal range.
- Laboratory data for subjects with values outside the normal range.

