13.1 Pharmacodynamic Analyses

PD data will be summarized using the PD Analysis Set.

FXIIa-mediated kallikrein activity will be assessed for the PD of CSL312 as described in Section 8.1.2 of the protocol.

FXIIa-mediated kallikrein activity will be listed by individual subjects and will be summarized by nominal time points, study subpopulation and actual treatment.

FXIIa-mediated kallikrein activity % of Baseline values will also be provided in the listings, summaries, and figures. The % of Baseline values will be derived as $100 \times \text{visit value} / \text{baseline value}$.

The same summaries and figures, including subgroup analyses, as described for the PK analysis (see [Section 12.1](#)) will be generated for FXIIa-mediated kallikrein activity and FXIIa-mediated kallikrein activity % of Baseline values.

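### Laboratory and vital-sign changes from baseline pool on-drug with drug-free baselines, because rollovers previously given CSL312 take their baseline at entry to this study

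*SAP*

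**What the plan says.** SAP 8.2.3 gives one definition for all subjects: "Baseline is defined as the most recent, non-missing value prior to first study drug administration in this study". It makes no exception for rollovers.

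Protocol 4.1.1.2 lets subjects who complete either lead-in study enter without washout: they "may roll over directly from treatment in those trials and start this study at Treatment Day 1". Their Day 1 values are the last lead-in values. Under Protocol 8.6.3, "assessments from Day 182 of Study CSL312_3001 will be used to fulfill assessments for Day 1 of Study CSL312_3002". Under Protocol 8.6.4, "assessments from Week 57 (Day 399) of Study CSL312_2001 will be used to fulfill assessments for Day 1 of Study" CSL312_3002.

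For laboratory data, SAP 11.5 plans "Laboratory values and changes from baseline by scheduled study visit for continuous tests and number and percentages per category for categorical tests". SAP 11.6.1 plans the same kind of change table for vital signs. Neither has a row in Table 5 (SAP 17), so neither is split by earlier exposure to CSL312.

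For pharmacodynamics, SAP 13.1 says: "FXIIa-mediated kallikrein activity % of Baseline values will also be provided in the listings, summaries, and figures". It applies the PK subgroup analyses to this measure. SAP 12.1 lists treatment-naïve subjects among those subgroups, and the PD row of Table 5 is marked for the treatment-naïve / non-treatment-naïve split.

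For WPAI:GH, TSQM II and AE-QoL, SAP 10.3.2.1 says the analyses "will be only performed separately for treatment-naïve subjects and non-treatment-naïve subjects", and describes this as a departure from its other analyses.

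**The concern.** A change from baseline shows a drug effect only if the baseline was taken off the drug. For a subject who has been on CSL312 for months, the value before the first dose in CSL312_3002 already contains whatever the drug does. Later values should then differ little from it. Averaged with treatment-naïve subjects, whose baseline is drug-free, these near-zero changes pull the pooled mean toward no change.

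The study's primary objective is long-term safety. The laboratory panel includes aPTT, prothrombin time, INR and D-dimer, the drug inhibits FXIIa, and thromboembolic and bleeding events remain AESIs. A coagulation shift, if there were one, would look smaller in the pooled change table than it is in people starting the drug. The SAP keeps the two groups apart for the quality-of-life scores but not for laboratory and vital-sign changes, where the same arithmetic applies.

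**Working it through.** **Plan's own figure.** The documents state no dilution figure and no rollover share. The one design figure (100 subjects, 3%, 95% confidence) reproduces, 1 − 0.97^100 = 0.952, but does not bear on this point.

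**Who has an on-drug baseline.**
- CSL312_2001 rollovers: all. SAP 8.3.2 says none of them is a placebo subject.
- CSL312_3001 active-arm rollovers: all.
- CSL312_3001 placebo rollovers: none. SAP 8.3.2 classes them as treatment-naïve.
- Newly enrolled subjects: none.

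With the half-life of about 19 days (Protocol 1.2.3.1), and assuming 28 to 30 days between the last lead-in dose and Day 1, the fraction of drug remaining is 0.5^(28/19) = 0.36 to 0.5^(30/19) = 0.33. About a third is still present, on top of accumulation from earlier doses.

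**Formula.** Let f be the share of the pooled set with earlier CSL312 exposure and D the mean change in treatment-naïve subjects. If previously treated subjects are at steady state, their change is about 0, and

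pooled change = (1 − f) × D + f × 0 = (1 − f) × D.

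**Inputs for f.** 36 subjects completed CSL312_2001 (Protocol 1.2.3.2); 64 were randomised in CSL312_3001 (same section); about 150 are planned here (Protocol 3.5). The CSL312_3001 allocation and the number rolling over from each study are not given, so both are varied:

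f = r × (36 + 64 × a) / 150, with a = active share of CSL312_3001 and r = rollover fraction.

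The last column takes the protocol's figure of about 50% kallikrein inhibition at 200 mg (Protocol 3.3.2): pooled percent of baseline = 50 × (1 − f) + 100 × f.

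| Assumed active:placebo in CSL312_3001 | f, r = 1 | Share of D retained | f, r = 0.8 | Pooled kallikrein, % of baseline (r = 1) |
|---|---|---|---|---|
| none active (lower bound) | 36/150 = 24% | 76% | 19% | 62% |
| 1:1 | 68/150 = 45% | 55% | 36% | 73% |
| 3:2 | 74.4/150 = 50% | 50% | 40% | 75% |
| 2:1 | 78.7/150 = 52% | 48% | 42% | 76% |
| 3:1 | 84/150 = 56% | 44% | 45% | 78% |
| all active (upper bound) | 100/150 = 67% | 33% | 53% | 83% |

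The first and last rows are arithmetic limits, since CSL312_3001 had both arms.

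**The mix also differs by visit.** CSL312_2001 subjects have no haematology, biochemistry or coagulation at Month 3 (Protocol 8.6.4.2) but do at Month 6 (8.6.4.3); the other subjects have both (8.6.3.3, 8.6.3.4). With full rollover, no drop-out and 1:1 to 3:2 allocation, f for these tests is 32/114 = 28% to 38.4/114 = 34% at Month 3, and 45% to 50% at Month 6. The pooled change would fall from 66–72% to 50–55% of D with no subject changing, which could be taken for a fading effect.

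**After splitting.** The treatment-naïve column keeps all of D (kallikrein about 50% of baseline). The non-treatment-naïve column shows about no change (about 100%), correctly labelled as change during this study.

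**The case against.** Most of the laboratory safety reporting does not use baseline. The secondary endpoint is laboratory findings reported as AEs. SAP 11.5 also gives absolute values by visit, clinically significant findings by test and visit, and listings of out-of-range values. No confirmatory test is planned, and a baseline at entry to this study is a legitimate description of change during this study. All of that stands, and it limits the point to the change columns of descriptive tables. The absolute values do not cure it, though, because the pooled Day 1 mean is itself a mixture of on-drug and drug-free values.

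Several stronger readings are tempting, and the documents do not support them:

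- *Every rollover has an on-drug baseline.* CSL312_3001 placebo rollovers do not. Counting them in would always give the 67% upper bound.
- *Changes are diluted by about half.* A share of 45% to 55% needs 68 to 82 of 150 subjects with earlier exposure: with all 36 from CSL312_2001, 32 to 46 of the 64 from CSL312_3001. That is plausible but cannot be derived from the documents.
- *The kallikrein effect would be hidden.* An undiluted treatment-naïve result is already planned; only the overall percent-of-baseline table is mixed.
- *The study will under-report laboratory shifts in the product's favour.* Dilution matters only where the drug moves the parameter. No laboratory or vital-sign effect is documented. Protocol 3.3.2 does not expect aPTT prolongation in most subjects, and Protocol 1.2.3.1 reports no clinically significant haematology or chemistry trends in the first healthy-volunteer study.
- *The SAP recognised the problem for quality of life and ignored it elsewhere.* SAP 10.3.2.1 separates the groups but gives no reason.

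**Conclusion.** The concern holds in limited form. For rollovers previously given CSL312 the baseline is an on-drug value, and the laboratory and vital-sign change tables pool them with treatment-naïve subjects. Any drug effect in those tables shrinks by the previously treated share: 24% to 67% under full rollover, 19% to 53% at 80% rollover. The direction, toward no change, is certain if an effect exists; the size is not known. The range assumes about 150 enrolled and previously treated subjects at steady state.

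A reader might infer that the main safety or efficacy results are compromised. They are not. Baseline does not enter the TEAE counts of the primary endpoint or the laboratory findings reported as AEs. Attack-rate reduction uses the Run-in Period, taken from the lead-in study for rollovers. This is a flaw in descriptive safety tables that is worth correcting, and no more than that.

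**What to change.** Before database lock:

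1. Present the laboratory (SAP 11.5) and vital-sign (SAP 11.6.1) change-from-baseline tables by treatment-naïve and non-treatment-naïve status, as SAP 8.3.2 already defines them, and add both rows to Table 5.
2. State in SAP 13.1 that kallikrein percent of baseline is to be read from the treatment-naïve stratum, not from the pooled table.
3. Optionally, where comparable lead-in data exist, add a supplementary change from the last value before the first-ever CSL312 dose. There is a precedent for using lead-in data: Run-in on-demand medication for rollovers "will be imported from the final analysis datasets of the respective lead-in study" (SAP 9.4). This should not replace the main baseline. For CSL312_2001 subjects it would span earlier periods on other regimens or placebo (Protocol 1.2.3.2), and the documents do not describe lead-in laboratory schedules or assays.

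Items 1 and 2 need SAP wording and stratified versions of existing tables, with smaller numbers per column and no new data. Item 3 needs an extra import and a comparability check whose size the documents do not allow one to judge.
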